6.8. Study Outcomes

Primary outcome

Functional outcomes defined as a shift (improvement) in scores on the mRS at 90 days (3 months). The mRS is a widely used instrument for grading the impact of stroke treatments, with scaling of: 0 = no symptoms at all; 1 = no significant disability despite symptoms, but able to carry out all usual duties and activities; 2 = slight disability, unable to carry out all

previous activities but able to look after own affairs without assistance; 3 = moderate disability requiring some help, but able to walk without assistance; 4 = moderate-severe disability, unable to walk without assistance and unable to attend to own bodily needs without assistance; 5 = severe disability, bedridden incontinent, and requiring constant nursing care and attention; 6 = dead.

Secondary outcomes are:

- 1) ICH: a) sICH, based on National Institutes of Neurological Diseases and Stroke (NINDS) criteria of brain imaging (or necropsy) confirmed ICH with ≥ 1 points deterioration in NIHSS score or death within 36 hours from baseline; b) sICH, defined by Safe Implementation of Thrombolysis in Stroke-Monitoring Study (SITS-MOST) criteria, as large ('type II') parenchymal ICH with ≥ 4 points decline in NIHSS score or death within 36 hours from baseline; c) sICH, defined by the new Heidelberg Bleeding Classification (HBC) criteria; d) ICH of any type in brain imaging ≤ 7 days of treatment; e) any symptomatic ICH (sICH) after MT within 90 days. ICH will be assessed by CT imaging and adjudicated centrally.³³
- 2) Imaging endpoints: a) infarct size growth assessed by MRI at 48 hours; b) edema volume assessed by CT at Day 7.
- 3) Death or dependency measured by NIHSS at 7 days;
- 4) The followings at 90 days: Death or major disability (mRS 3-6); separately on death and disability (mRS 3-5); health-related quality of life (HRQoL) using EQ-5D; duration of hospitalisation; residence and hospital service cost.

6.9 Economic Evaluation

Economic evaluation provides value judgement for health policy makers when they consider to scale-up the health intervention. In ENCHANTED2 trial, the intervention of BP lowering will be initiated after successful recanalization and the BP target will be maintained for at least 3 days (or hospital discharge if earlier). Since an increasing number of patients receive MT annually, it is important to know whether the ENCHANTED2 is cost effective compared to the conventional care. A within-trial economic evaluated will be conducted to compare the incremental costs including costs of intervention and difference in health service cost versus the incremental effectiveness which is expressed using quality-adjusted life years (QALYs). The (trial-based) incremental cost effectiveness ratio will be calculated and then compared to the willingness-to-pay threshold in China and other countries to determine the cost-effectiveness of ENCHANTED2. The economic evaluation will be conducted from the healthcare payer's perspective.

6.10 Data Collection and Follow-up

Registration, baseline assessment, and randomisation should be achieved over 15 minutes. Doctor/nursing attendance with the randomised patient is likely to be required for 1-2 hours post-randomisation to ensure the titration of BP lowering in the active group, and consistent BP recordings. All patients are followed daily for 1 week, and then 90 days unless death occurs earlier. Key demographic and clinical data will be collected at randomisation. Follow-up data will be collected on 3 occasions: 24 hours, 7 days (or hospital discharge if sooner), and 90 days. The 90 day evaluations will be conducted in-person or by telephone, by a trained staff member at the local site who is blind to the treatment allocation. Brain imaging (CT scan and/or MRI, with any associated diffusion/perfusion and angiogram images) will be conducted according to standardized techniques at baseline, within 24-48 hours (ie next day follow-up scan), and at a later stage in all surviving patients who may deteriorate or for other clinical

reason during follow-up. Brain imaging (CT scan and/or MRI) must be uploaded to the ENCHANTED2 server, either directly from the hospital site (if they have suitable broadband internet) or via the RCC office, to be analyzed centrally for measurement of any ICH or haemorrhagic complications of the ischemic lesion, and for future measurement of areas of infarction, ischemic penumbra, and site of LVO. The LCC will keep a hard copy in an uncompressed DICOM format onto a CD-ROM for monitor site verification (**see Appendix 3**). Trial management is facilitated by an established internet-based system.

All randomised patients will be followed up to 90 days, or death if prior to 90 days. Patients who do not follow the protocol and/or discontinue allocated management should still be followed up to 90 days as their data will be analyzed on the 'intention to treat' principle. **Table 3** illustrates the schedule and nature of the data collection required during the study period. The paper version of the case reports forms (CRFs) will be supplied with the procedure manual, as a reference only, together with a guide to completion of each data element and a definition of terms.

All data entry will be completed on a password protected study website. This web-based data management system will allow for real time data query generation for values entered outside of pre-set valid ranges and consistency checking. This system will speed up data reporting and assist overall trial management for all participating centres. In addition to the web-based data entry, BP and drug usage will also be recorded on a paper CRF at the patient's bedside as part of the patient's usual medical record management.

6.10.1 Screening Logs

Each site should keep log of all AIS patients with LVO confirmed by brain imaging arriving <24 hours of symptom onset (or last known well) and who were considered for the study but subsequently excluded. The screening log will record patients' initials and date of admission together with a brief description of the main reason as to why a patient was not randomised. The log will be used by the Research Coordinator, PI and the CCC to monitor recruitment and to identify specific barriers to randomisation of eligible patients. It is also a requirement for the reporting of results of clinical trials.

6.10.2 Patient Contact Details Log

Each centre will keep a record of the contact details and information of next-of-kin for all randomised patients. This will be kept at the participating centre in a locked filing cabinet and in accordance with local policies on the custody of confidential clinical trial data. The Patient Contact Details Log will also be used to document any issues arising from the consent procedure, attempts at follow up and information on protocol violations. The Patient Contact Details Log will be used by the Research Coordinator and PI in managing the consent process, follow-up schedule, and in responding to queries from the CCC.

6.10.3 Randomisation Assessment (Form A)

All AIS patients obtaining successful recanalization after MT will be assessed by the responsible physician for eligibility to the study using a checklist of the eligibility criteria described previously. This form will be kept at the participating site in a locked filling cabinet with the study patient's file.

6.10.4 Baseline Data (Form B)

The following information is to be collected on admission:

- BP, Heart rate (HR) and blood glucose (BG) at admission
- Demography, and medical history

- Medications at time of admission
- Baseline GCS and NIHSS scores
- Initial brain imaging (CT and/or MRI)
- Other imaging (CTA/MRA, CTP/MRP, DSA)
- Management with rt-PA if performed
- Details of MT procedure: anesthesia methods, use of GP IIb/IIIa receptor inhibitors, MT device(s) and their sequence, number of retrieval attempts, door-to-puncture time (DPT), onset to reperfusion time, TICI score after MT, NIHSS score after MT.
- Baseline blood tests and electrocardiogram (ECG)
- Pattern of neurological deficits

6.10.5 Follow up Data

Day 1 (Form C)

The primary goal of assessments within the first 24 hours will be to ensure adherence to the allocated the protocol. BP and administered medication will be recorded. BP will be recorded supine in the non-paretic arm from the automated, electronic device used at the Clinical Centre. BP will be recorded every 15 minutes for the first hour, then hourly for the next 5 hours, and 6 hourly from 6 hours to 24 hours. When i.v. boluses are given, HR and BP should be re-checked and recorded 5 and 15 minutes later. The following information will be recorded.

- BP
- BP lowering medication
- GCS and NIHSS scores at 24 hours
- Follow up brain imaging (CT brain and/or MRI) should be undertaken at 24-48 hours post-MT
- If other imaging investigations are performed (i.e. transcranial Doppler), these should be documented in the CRFs
- Antithrombotic medications
- Follow up blood tests
- Standard stroke care assessment

Day 7 or discharge if earlier (Form D)

On Day 7 or on the day of hospital discharge/transfer or death if prior to Day 7, the contact details of the patient or caregiver should be confirmed to facilitate follow up assessments. The following information will be recorded:

- GCS and NIHSS score
- Dependency assessed with the mRS
- BP
- BP lowering medication (medications used during Days 2 to 7)
- Medications and key specific treatment received during hospitalization
- Other aspects of acute stroke management during hospitalization

- Prognosis prediction from clinicians
- Date of discharge or transfer from hospital
- Repeat brain CT or MRI
- Healthcare costs and details of blood pressure lowering treatment.

BP Monitoring Chart (Form E)

As usual nursing care during the study period, the BP assessments in 7 days will be used to check adherence to BP management protocol.

Day 90 Follow-up (Form F)

These assessments are to be undertaken by an investigator who was not involved in the clinical management of the patient, and blind to the randomised treatment allocation. On 90±7 days, all surviving patients will be evaluated through a telephone interview or at a face-to-face consultation.

Detailed resource utilization data, hospital billing data, physical function and patient reported quality of life data were collected for patients from the time of randomisation through 90-day follow-up. These data were used to calculate direct healthcare costs and QALY during the initial 90-day period based on international and national guidelines.^{34, 35}

- BP
- Dependency assessed with the mRS³⁶
- HRQoL measured by the EQ-5D³⁷
- Patient living status (e.g. home, high care)
- Any complications or hospitalization since going home
- Any medication currently used
- Healthcare related cost.

Death

Patients who have died prior to any of the above scheduled assessments, cause of death documentation will be collected with date and time of death. Copies of post-mortem reports, hospital record entry or death certificate, should be kept with the Patient Contact Details log to assist in trial monitoring by the CCC. An SAE form is to be completed for all deaths during the study period, stating the primary and underlying cause of death.

Withdrawal of allocated management and protocol violations

A form will be provided to record the date and circumstances surrounding any deviation from the protocol or missed assessments.

Consent

Consent will be documented in the patient's progress notes and CRF and the type(s) of consent obtained will also be recorded on the database.

Serious Adverse Events (SAEs)

All SAEs will be recorded on the SAE form, and completed on the electronic CRF or faxed/mailed from a printed form to the CCC within the prescribed time. Additional information may be requested to provide supplementary information on the event and outcome.

Table 2 Schedule of evaluations

Evaluation	Baseline (Prior Randomisation)	Day			365 ^b
		1	7 ^a	90 ^b	
Eligibility	X				
Brain imaging (CT ± angiogram or MRI± angiogram or DSA)	X	X	X		
BP	X (BP x 2)	X** q 15 min 1h 6h	X q12h	X	
HR	X				
ECG	X				
Consent	X				
Medical history, prior medications	X				
Details of rt-PA (if performed) and MT	X				
Physical exam GCS/ NIHSS	X	X	X		
Functional assessment with mRS	X		X	X	
HRQoL assessment with EQ-5D				X	
Routine blood tests	X	X			
BP lowering treatment		X	X	X	
Antithrombotic and other medications		X	X	X	
Standard stroke care		X	X		
Hospitalized or not			X	X	
Contact details for Follow-up		X	X		
Hospital service cost			X	X	
SAEs	X ^c	X	X	X	X

** At any point where intravenous antihypertensive agents are administered, BP and HR should be recorded 5 and 15 minutes later.

(a) Or the day of discharge if prior to day 7.

- (b) Information collected at a face to face consultation or through a telephone interview.
- (c) After informed consent.

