17. APPENDIX

Appendix 1 - BP management protocol

Appendix 1A - BP protocol for centres with Urapidil (China)

Intensive BP lowering group	TREATMENT PROTOCOL
INITIAL therapy	
BP Target	SBP <120mmHg achieved within 1 hour after randomisation
Monitoring	
 Continuous HR monitoring Record BP/HR q 5 mins during active treatment, then q 15 min for first hour, q 30 min for next 5 hours and then hourly to 24 h
Urapidil (IV)	
 If SBP \geq 120 mmHg and HR >55 bpm, repeat 10-25 mg IV bolus q5 mins until target SBP reached (<120mmHg) or HR <55 bpm If HR increases by >15 bpm or is >90 bpm, add IV beta blocker
Hydralazine (IV)	
 Hydralazine test dose: 5 mg IV bolus over 1 minute If SBP \geq 120 mmHg, repeat 5 mg IV bolus in 5 minutes If SBP still \geq 120mmHg, give 10 mg IV bolus q 5 mins until target SBP reached Increase to 20 mg bolus if required Maximum hydralazine dose = 240mg
Glyceryl Trinitrate (topical)	
If BP persistently \geq 120 mmHg:
 
 ADD topical glyceryl trinitrate (paste or patch) at a rate of 5-10 mg/24 hour 
(\approx 200-400 μg/hour). NB: also known as topical nitroglycerin

Continuous IV Infusions (requires ICU admission)	
If BP persistently \geq 120 mmHg:
 
 Urapidil infusion 5-30 mg/hour If target still not reached ADD infusion of hydralazine 50-150 μg/min OR glyceryl trinitrate 1-100 μg/Kg/min
MAINTENANCE therapy	
BP Target	Maintenance of SBP 100-120 mmHg
Monitoring	Once SBP is under target (confirmed by 4 readings 15 minutes apart): 
 Record BP/HR q 30 minutes for 5 hours and then q 1 h for 18 h
IV treatment prn	
If SBP exceeds 120mmHg at any point:
 
 Give Urapidil (10-25 mg) and/or hydralazine (10-20 mg) boluses. BP and HR should then be recorded 5 and 15 minutes later If SBP is 100-120mmHg, Urapidil 10-25 mg (dose dependent on initial response) should be administered q 6 hours for the first 24 hours after symptom onset (total of 3 doses) If SBP \leq 100 mmHg, cease therapy If HR increases by >15 bpm or is >90 bpm, add IV beta blocker Note: urapidil and hydralazine may be used together during the maintenance phase

Oral treatment

Start treatment by 24 hours (use nasogastric if required)

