**Table 4. Clinical and BP measures recorded during the first 24 hours**

Variable	Intensive BP lowering (N = )	Standard BP lowering (N = )	Total (N = )
NIHSS Score at 24 hours	xxx	xxx	xxx
Mean (SD)	xxx.x (xxx.x)	xxx.x (xxx.x)	xxx.x (xxx.x)
Median (Q1; Q3)	xxx (xxx; xxx)	xxx (xxx; xxx)	xxx (xxx; xxx)
min max	xxx to xxx	xxx to xxx	xxx to xxx
GCS Score at 24 hours	xxx	xxx	xxx
Mean (SD)	xxx.x (xxx.x)	xxx.x (xxx.x)	xxx.x (xxx.x)
Median (Q1; Q3)	xxx (xxx; xxx)	xxx (xxx; xxx)	xxx (xxx; xxx)
min max	xxx to xxx	xxx to xxx	xxx to xxx
Highest SBP (mmHg)	xxx	xxx	xxx
Mean (SD)	xxx.x (xxx.x)	xxx.x (xxx.x)	xxx.x (xxx.x)
Median (Q1; Q3)	xxx (xxx; xxx)	xxx (xxx; xxx)	xxx (xxx; xxx)
min max	xxx to xxx	xxx to xxx	xxx to xxx
Highest DBP (mmHg)	xxx	xxx	xxx
Mean (SD)	xxx.x (xxx.x)	xxx.x (xxx.x)	xxx.x (xxx.x)
Median (Q1; Q3)	xxx (xxx; xxx)	xxx (xxx; xxx)	xxx (xxx; xxx)
min max	xxx to xxx	xxx to xxx	xxx to xxx
Lowest SBP (mmHg)	xxx	xxx	xxx
Mean (SD)	xxx.x (xxx.x)	xxx.x (xxx.x)	xxx.x (xxx.x)
Median (Q1; Q3)	xxx (xxx; xxx)	xxx (xxx; xxx)	xxx (xxx; xxx)
min max	xxx to xxx	xxx to xxx	xxx to xxx
Lowest DBP (mmHg)	xxx	xxx	xxx
Mean (SD)	xxx.x (xxx.x)	xxx.x (xxx.x)	xxx.x (xxx.x)
Median (Q1; Q3)	xxx (xxx; xxx)	xxx (xxx; xxx)	xxx (xxx; xxx)
min max	xxx to xxx	xxx to xxx	xxx to xxx

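### Protocol gives two conflicting first-day BP schedules for the intensive arm (12 and 32 readings), and SAP Table 4 does not say which readings define the highest and lowest values

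*Protocol*

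**What the plan says.** **All patients.** The Day 1 entry in Protocol 6.10.5 (Form C) has no arm restriction. It starts with quarter-hourly readings over one hour; the rest of the day runs "then hourly for the next 5 hours, and 6 hourly from 6 hours to 24 hours". A further rule covers intravenous dosing: "When i.v. boluses are given, HR and BP should be re-checked and recorded 5 and 15 minutes later". Table 2 abbreviates this schedule, and its footnote repeats the checks after intravenous treatment. Form E is a nursing chart with no stated frequency; "the BP assessments in 7 days will be used to check adherence to BP management protocol".

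**Intensive arm.** The monitoring rows of Appendices 1A to 1E require recording every 5 minutes during active treatment, "then q 15 min for first hour, q 30 min for next 5 hours and then hourly to 24 h". The maintenance rows start after four confirming readings 15 minutes apart: "Record BP/HR q 30 minutes for 5 hours and then q 1 h for 18 h".

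**Control arm.** Appendix 1G contains treatment rules and no monitoring row.

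**Analysis.** SAP Table 4 summarises the highest and lowest systolic and diastolic pressure of the first 24 hours by arm (for example, the row "Lowest SBP (mmHg"). It does not say which readings enter. SAP 3.6 weights for uneven spacing, but only in the mixed-model estimate of the mean.

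**The concern.** An intensive-arm patient is subject to two recording schedules that cannot both be the rule. The difference is largest from 6 to 24 hours, where scheduled readings are 6 hours apart in one text and 1 hour apart in the other.

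The statistical consequence concerns the extremes. The minimum of a series falls, and the maximum rises, as more readings are taken, even when the underlying pressure is the same. If one arm is measured more often, a between-arm comparison of lowest values mixes the treatment effect with measurement frequency. Weighting for spacing can correct a mean but not a minimum or maximum. At stake is a safety-relevant description: Protocol 6.7 sets a systolic pressure of 100 mmHg as the threshold for ceasing therapy in the intensive arm, and readers will look at Table 4 to see how low pressures went.

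**Working it through.** **1. Count the scheduled readings after randomisation.**

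| Period | Form C | Appendices 1A to 1E |
|---|---|---|
| 0 to 1 h | 4 | 4 |
| 1 to 6 h | 5 | 10 |
| 6 to 24 h | 3 | 18 |
| Total | 12 | 32 |

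The ratio is 32/12 = 2.67, before any 5-minute readings. The maintenance rows give the same total: 4 + 10 + 18 = 32. All 12 Form C times are contained in the 32.

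**2. Extra readings within Form C itself.** Each intravenous bolus adds 2 recorded readings in either arm. Appendices 1A to 1D schedule up to 3 maintenance boluses in the intensive arm when systolic pressure is already 100 to 120 mmHg, so up to 3 × 2 = 6 extra readings before any titration boluses. Appendix 1G calls for acute intravenous therapy above 180 mmHg and allows BP lowering only above 150 mmHg. The extra readings should therefore fall mostly in the intensive arm, and they follow a dose.

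**3. Size if all scheduled readings are used.** The documents state no figure to reproduce and give no within-patient SD or correlation, so the inputs here are assumptions. Each setting used 40,000 simulated patients, with the same true pressure course read on both schedules. The shift is the mean extreme over 32 readings minus the mean extreme over 12.

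- *Simple case.* Independent readings, SD 10 mmHg, flat course: the mean extreme lies 20.7 mmHg from the patient's mean with 32 readings and 16.3 with 12, so the shift is 4.4 mmHg.
- *Flat course, correlated readings.* SD 10 to 15, 30% of the variance as reading noise, the rest with exponential correlation (time constant 0.5 to 3 h): the lowest value is 4.2 to 6.9 mmHg lower with 32 readings. Over a wider range (SD 8 to 15, time constant up to 4 h, other noise shares) the shift in the extremes is 2.7 to 6.9 mmHg.
- *Falling course, closer to the intensive arm.* Same noise model, mean pressure falling from 150–160 to 115 mmHg with a decay constant of 0.25 to 1 h: the lowest value is about 4.6 to 9 mmHg lower.
- *Highest value on the falling course.* The shift is 0.0 to 2.0 mmHg when the randomisation reading is included and about 0.2 to 5.6 mmHg when it is not. The peak usually falls early, where the two schedules coincide.

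These settings leave out the 5-minute and post-bolus readings.

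**4. After the fix.** If both arms use only the shared times, the shift caused by the schedule is 0.

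**The case against.** The strongest reply is that Form C is the data-collection schedule and applies to both arms, while the appendices are bedside titration instructions. Protocol 6.10 separates web data entry from the bedside paper record. The visible rows of SAP Table 8 (15, 30 and 45 minutes, 1 hour, 2 hours) match the Form C grid for both arms; half-hourly capture would show a row at 1.5 hours. If Table 4 draws only on those times, the schedule produces no bias. This stands: a reader might infer that Table 4 is biased as planned, and the documents do not establish that. They do not exclude it either. Nothing ties Table 4 to the Table 8 grid, and the post-bolus readings are part of Form C.

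Three other strong readings are not supported.

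- *That the highest value is inflated as much as the lowest is depressed.* This needs a stable mean. Intensive patients enter at 140 mmHg or above and are to be brought below 120 within an hour.
- *That lowest systolic pressure is the trial's designated measure of over-treatment.* No passage says so. Protocol 7.1 and 7.2.3 rely on monitoring-board review of BP differences and on serious adverse events, with severe hypotension as an example.
- *That intensive patients on intravenous drugs would go unobserved for 6 hours.* Form C sets what is recorded, the post-bolus checks still apply, and Protocol 6.7 ties titration to regular monitoring.

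It is also fair to object that counting hypotension only at the shared times would hide genuine low readings after a bolus. The fix below avoids that.

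**Conclusion.** The contradiction between Form C with Table 2 and Appendices 1A to 1E is certain: 12 against 32 scheduled readings, and 3 against 18 from 6 to 24 hours, with no control-specific schedule. The passages must be reconciled; this review takes no position on which frequency is right.

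The effect on Table 4 is conditional. If all recorded readings feed it, the intensive arm's lowest systolic pressure will be about 4 to 9 mmHg lower from measurement frequency alone, under the assumed SD of 10 to 15 mmHg and the assumed correlation and BP course. The effect on the highest value is probably small, provided the randomisation reading counts and pressure starts well above target. Table 4 has no difference, interval or test. The primary outcome and the mixed-model BP mean are not affected by this mechanism. This is a cheap improvement to a descriptive table plus a necessary protocol clarification.

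**What to change.** 1. **Protocol.** Reconcile 6.10.5, Table 2 and the monitoring rows of Appendices 1A to 1E, state what applies to controls (Appendix 1G is silent), and say which readings enter the study database.
2. **SAP 3.6 and Table 4.** Derive the between-arm highest and lowest systolic and diastolic values from the scheduled times common to both arms: randomisation plus the 12 Form C times, or whatever shared set the reconciliation produces.
3. **Alongside, in the same table.** Show the extremes from all recorded readings and any counts of low BP, with the number of readings per patient by arm, so that no low reading leaves the safety report.

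The cost is a protocol clarification, one derivation rule and a few table rows. No new data are needed, since Form C already requires the shared times in both arms. The downside is that brief extremes between common times appear only in the all-readings summary.
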